4.2.5 PFS sensitivity analyses for the 3 primary patient populations

The following PFS sensitivity analyses will be considered:

- ascertainment bias: refers to possible bias introduced by disagreement between site investigator and BICR assessments and subsequent informative censoring in PFS analyses of the BICR data.
- evaluation-time bias: refers to the possibility that the PFS effect is partly an artefact of one arm being assessed more frequently
- attrition bias: refers to the possibility that the rate and nature of censoring has resulted in bias

Ascertainment bias

The primary analyses of PFS will be repeated using investigator assessed RECIST data. The p-value from the stratified log-rank test, and the HR and 90% CI from the stratified proportional hazards model will be presented for each pairwise comparison.

Disagreements between investigator and central reviews of RECIST progression will be presented for each treatment group. The summary will include the early discrepancy rate which is the frequency of central review declared progressions before the investigator review as a proportion of all central review progressions and the late discrepancy rate which is the frequency of central review declared progressions after the investigator review as a proportion of all discrepancies.

If there is an important discrepancy between the primary analysis using BICR RECIST-based data and this sensitivity analysis using the site investigator RECIST-based data then the proportion of patients with site but no central confirmation of progression will be summarised; such patients have the potential to induce bias in the BICR RECIST-based PFS analysis due to informative censoring. An approach of imputing an event at the next visit in the central review analysis may help inform the most likely HR value (Fleischer et al 2011), but only if an important discrepancy exists between site investigator and BICR data exists. Note: it is the blinded study team's responsibility to determine whether there is an important discrepancy upon blinded review of the data, and whether such further analyses are required.

Evaluation-time bias

A sensitivity analysis will be performed to assess possible evaluation-time bias that may be introduced if scans are not performed at the protocol-scheduled time points. The midpoint between the time of progression and the previous evaluable RECIST assessment (using the final date of the assessment) will be analysed using a stratified log-rank test, as described for the primary analysis of PFS. Note that midpoint values resulting in non-integer values should be rounded down. For patients whose death was treated as a PFS event, the date of death will be used to derive the PFS time used in the analysis. This approach has been shown to be robust to even highly asymmetric assessment schedules (Sun and Chen 2010). The p-value from the stratified log-rank test, and the HR and 90% CI from the stratified proportional hazards model will be presented for each pairwise comparison.

To support this analysis, the patient-level mean inter-assessment times, will be summarised using descriptive statistics for each treatment, separately for assessments up to Week 72 and post-Week 72. This approach will use the BICR RECIST assessments.

Attrition bias

Attrition bias will be assessed by repeating the PFS analysis except that the actual PFS event times, rather than the censored times, of patients who progressed or died in the absence of progression immediately following two, or more, non-evaluable tumour assessments will be included. In addition, and within the same sensitivity analysis, patients who take subsequent therapy (note that for this analysis radiotherapy is not considered a subsequent anti-cancer therapy) prior to their last evaluable RECIST assessment or progression or death will be censored at their last evaluable assessment prior to taking the subsequent therapy. The p-value

from the stratified log-rank test, and the HR and 90% CI from the stratified proportional hazards model will be presented for each pairwise comparison.

This analysis will be supported by a Kaplan-Meier plot of the time to censoring using the PFS data from the primary analysis and where the censoring indicator of the PFS analysis is reversed.

Additional supportive summaries

In addition, the number of patients prematurely censored (see definition below) will be summarised by treatment arm. A patient would be defined as prematurely censored if they had not progressed (or died in the absence of progression) and the latest scan prior to DCO was more than one scheduled tumour assessment interval plus 2 weeks prior to the DCO date.

Additionally, summary statistics will be given for the number of days from censoring to DCO for all censored patients.

A summary of the duration of follow-up will be summarised using median time from randomisation to date of censoring (date last known to have not progressed) in censored (not progressed) patients only, presented by treatment arm.

Additionally, summary statistics for the number of weeks between the time of progression and the last evaluable RECIST assessment prior to progression will be presented for each treatment arm.

Summaries of the number and percentage of patients who miss two or more consecutive RECIST assessments will be presented for each treatment arm. In addition, a summary of new lesions (i.e. sites of new lesions) will be produced.

4.2.6 PFS subgroup analyses

Subgroup analyses will be conducted comparing PFS between two treatment arms in the following subgroups of the FAS, separately within each of the 3 primary patient populations:

- prior platinum treatment (no versus yes)
- Sex (male versus female)
- Age at randomisation (<65 versus ≥ 65 years of age), see Section 3.1.2 for handling of patients with a missing age at randomisation.

The subgroup analyses for the stratification factor (prior platinum treatment) will be based on the values entered into the IVRS, all other factors will be based on values recorded on the eCRF as indicated above.

No adjustment to the significance level for testing will be made since all these subgroup analyses will be considered exploratory and may only be supportive of the primary analysis of PFS.

For each subgroup level of a factor, the HR and 90% CI will be calculated from an unstratified Cox proportional hazards model with treatment as only covariate. These HRs and associated 2-sided 90% CIs will be summarised and presented on a forest plot, along with the results of the overall primary analysis. In a forest plot the hazard ratio is plotted on a log-scale and the hazard ratio from the primary analysis should also be plotted to enable comparison.

If there are too few events available for a meaningful analysis of a particular subgroup (it is not considered appropriate to present analyses where there are less than 10 PFS events in a subgroup category), the relationship between that subgroup and PFS will not be formally analysed. In this case, only KM curves will be provided.

4.2.7 Other secondary efficacy analyses

Other secondary efficacy analyses will be performed according to the overview below.

Patient Population	Outcome Measures	Analysis Method(s)

 • HRR_m • All 	PFS using BICR according to RECIST 1.1	Weighted proportional hazards model stratified by prior platinum-based therapy Weighted KM curves by treatment arm, overall and separately by prior platinum-based therapy Sensitivity analyses: 
 • unweighted stratified proportional hazards model and unweighted stratified log rank test • unweighted KM curves • analyses using site investigator assessments according to RECIST 1.1

 • BRCA_m • HRR_m • Non BRCA_m HRR_m • All • Non HRR_m 	Objective response using BICR according to RECIST 1.1	Logistic regression model with covariates study treatment and prior platinum-based therapy. Sensitivity analysis using site investigator assessments according to RECIST 1.1

Patient Population	Outcome Measures	Analysis Method(s)

 • BRCAm • Non BRCAm HRRm • Non HRRm 	DoR using BICR according to RECIST 1.1	
Expected duration of response (EDoR) will be derived for each treatment arm as the product of the proportion of patients responding to study treatment and the mean DoR in responding patients. Mean and standard error of DoR in responding patients will be estimated using a suitable parametric model. For pairwise comparisons of treatment arms the ratio of EDoRs and its 90% CI will be estimated.
 
DoR in responding patients will be estimated by KM curves by treatment arms.
 
Sensitivity analysis using site investigator assessments according to RECIST 1.1

 • BRCAm • Non BRCAm HRRm • Non HRRm 	Percentage change in TL tumour size at Week 16 using BICR according to RECIST 1.1	
Parametric / non-parametric Analysis of Covariance model with
 
 • factor treatment arm • factor prior platinum therapy • covariate baseline TL tumour size • covariate time from baseline scan to randomisation. 
Sensitivity analysis using site investigator assessments according to RECIST 1.1

 • BRCAm • HRRm • Non BRCAm HRRm • All • Non HRRm 	Time to death for any cause	Same main analysis methods as described for analysis of PFS.

 • All 	Tumour and germline mutation status of CCl genes	Cross-tabulation summary of tissue HRR mutation status versus plasma HRR mutation status for each mutation type for all screened subjects with both tumour and plasma samples analysed.

4.2.8 PFS secondary analyses

4.2.8.1 PFS analyses based on BICR for patient population HRR_m

To achieve estimated pairwise HRs for PFS that are representative of the HRR_m patient population, the following approach will be implemented:

1. pairwise HRs (separately for patient population strata A and B) will be obtained from a proportional hazards model stratified for prior platinum-based therapy (no, yes)
2. a weighted estimate of the HR_{HRR_m} will be calculated using the estimated HR in patient population stratum A (HR_A) and the estimated HR in patient population stratum B (HR_B):
$$\ln(HR_{HRR_m}) = w_1 \ln(HR_A) + w_2 \ln(HR_B)$$
where weights w_1 and w_2 will be estimated from external literature and the study's screening records (the details of the weight estimation will be described in a separate appendix to the SAP)
3. For calculation of CIs, the overall variance (log scale) will take into account the variance of both groups (that are independent), and thus be calculated as:
$$\text{var}(\ln(HR_{HRR_m})) = w_1^2 \text{var}(\ln(HR_A)) + w_2^2 \text{var}(\ln(HR_B))$$

As sensitivity analyses,

- PFS will be analysed using an unweighted log rank test stratified for patient population (stratum A, stratum B) and prior platinum-based therapy (no, yes)
- pairwise HRs and CIs will be estimated from an unweighted proportional hazards model stratified for patient population (stratum A, stratum B) and prior platinum-based therapy (no, yes).

KM curves for PFS will be presented by treatment arm, overall and separately by prior platinum-based therapy (no, yes). These KM curves will be presented both in an unweighted manner (i.e., each patient receives the same weight of 1) and weighted by the weights for the two patient populations described above.

A sensitivity analysis of PFS using site investigator data will be performed.

4.2.8.2 PFS analyses based on BICR for patient population All

Similar summaries and weighted and unweighted analyses as described in Section 4.5.2.1 will be conducted for the All patient population; now with 3 weights to combine the HR estimates and its variances for the 3 patient population strata A, B and C.

A sensitivity analysis of PFS using site investigator data will be performed.

4.2.8.3 Analysis of objective response based on BICR for all five patient populations

Note: take into account the statement in Section 3.4.1 on the denominator when calculating percentages for ORR.

Frequency tables by treatment arm will be produced that present

- number and percentage of patients with / without objective response (the former is the ORR) according to BICR
- number and percentage of patients with / without objective response according to site investigator assessment.

Objective response will be analysed using logistic regression with covariates study treatment and prior platinum-based therapy (no/yes). The results of the analysis will be presented in terms of odds ratio comparing treatment arms in pairwise manner together with associated 90% profile likelihood CI (using the option 'LRCI' in SAS PROC GENMOD) and 2-sided p-value. P-values will be based on twice the change in log-likelihood resulting from the addition of covariate study treatment to the model containing only the covariate related to prior platinum-based therapy. The three pairwise odds ratio will be the following:

- objective response odds ratio for AZD6738+Olaparib over Olaparib alone
- objective response odds ratio for AZD1775+Olaparib over Olaparib alone
- objective response odds ratio for AZD6738+Olaparib over AZD1775+Olaparib.

If there are not enough responses for a meaningful analysis using logistic regression then a Fisher's exact test using mid p-values will be presented for each pairwise comparison of treatment arms. The mid-p-value modification of Fisher's exact test amounts to subtracting half of the probability of the observed table from Fisher's p-value, i.e., mid p-value = 2-sided p-value – table probability/2.

A sensitivity analysis of objective response using site investigator data will be performed.

4.2.8.4 Analysis of duration of response based in BICR for the 3 primary patient populations

In order to analyse the secondary outcome variable DoR between treatment arms, the expected duration of response (EDoR) will be derived for each treatment arm (Ellis et al 2008). The EDoR is the product of the proportion of patients responding to study treatment and the mean DoR in responding patients, so EDoR is based on all randomised patients within the respective patient population. The variance of EDoR, on a log-scale, is given in Ellis et al 2008. Mean and standard error of DoR in responding patients will be estimated using a parametric model in SAS PROC LIFEREG; Ellis et al 2008 provides formulae for the exponential, Weibull and log-normal distributions. The best fitting distribution will be selected during the blind data review and detailed in a SAP Amendment prior to respective unblinding.

For pairwise comparisons of treatment arms the ratio of EDoRs (including 90% CIs) will be estimated, using the selected probability distribution for DoR in responding patients. This EDoR analysis will be stratified by prior platinum therapy (no/yes), weighting each stratum inversely proportional to the within-stratum variance of the log of the ratio of EDoRs (see also Whitehead and Whitehead 1991):

- obtain stratum-specific estimates $\hat{x}_{i,no}$ and $\hat{x}_{i,yes}$ of EDoR for all 3 treatment arms $i=1,2,3$
- obtain stratum-specific treatment arm contrasts of the logs of the ratios of EDoRs:
 - contrasts $\ln \hat{x}_{i,no} - \ln \hat{x}_{j,no}$ for $i=1,2, i < j \leq 3$
 - contrasts $\ln \hat{x}_{i,yes} - \ln \hat{x}_{j,yes}$ for $i=1,2, i < j \leq 3$
- each overall pairwise treatment arm contrast will be obtained by combining the two stratum-specific treatment arm contrasts by weighting them inversely proportionately according to each within stratum variance and finally transformation to the original scale by applying the exp function.

Additionally, descriptive data will be provided for DoR in responding patients, including associated KM curves (including estimated median DoRs) and swimmer plots by treatment arm (without any formal comparison or p-value attached).

A sensitivity analysis of DoR using site investigator data will be performed.

4.2.8.5 Analysis of tumour size change at Week 16 based in BICR for the 3 primary patient populations

Absolute and percentage change from baseline in TL tumour size at Week 16 will be summarised and presented by treatment arm. The number and percentage of patients in each treatment arm whose Week 16 data is imputed will also be presented.

Percentage change in TL tumour size at Week 16 will be presented graphically using waterfall plots for each treatment arm: each patient's Week 16 percentage change in tumour size as a separate bar, with the bars ordered from the largest increase to the largest decrease. A reference line at the -30% change in TL tumour size level will be added to the plots, which corresponds with the definition of 'partial' response. All progressions will be marked with a '●' or designated with patterns or colours for overall response categories. The scale in these plots will be fixed to be from -100 to 100 to avoid presenting extreme values. Values that are capped as a result of this restriction to the scale are marked with '#'. Values are ordered in descending order with the imputations due to death appearing first followed by a gap followed by all other patients. Imputed values are clearly marked with '*' and patients with imputation where there was a death or evidence of progression have different shading to each other and the other patients to make it clear that these are different.

Pairwise treatment arm comparisons on percentage change in TL tumour size at Week 16 will be estimated from an Analysis of Covariance (ANCOVA) model including

- factor treatment arm
- factor prior platinum therapy (no/yes)
- covariate baseline TL tumour size
- covariate time from baseline scan to randomisation.

The number of patients, unadjusted mean and least squares means (lsmeans) for each treatment arm will be presented, together with the pairwise differences in lsmeans, 90% CIs and corresponding p-values.

A histogram of the residuals from fitting the ANCOVA model to the data (including both actual and imputed data) will be produced and used to assess whether ANCOVA is appropriate to analyse the data using percentage change in TL tumour size from baseline at Week 16. This decision will be made after unblinding when the model can be fitted. If ANCOVA assumptions are sufficiently met, these data will be analysed as described previously. If not, then the use of log-transformed data or a non-parametric approach will be used as described below.

If a log transformation of the data is decided, the percentage change in TL tumour size at Week 16 will be assessed as the natural logarithm of the ratio of the Week 16 TL tumour size over the baseline TL tumour size. Pairwise treatment arm comparisons on the log-transformed data will be performed with ANCOVA model as defined above (using covariate log-

transformed baseline TL tumour size). The ratios of the geometric least squares means (glsmeans), corresponding 90% CIs and p-values will be presented. In order to aid interpretation, the geometric mean ratios will also be presented as a percentage change from baseline (for example a glsmean of 0.8 would correspond to a 20% reduction).

In any case, an analysis of percentage change in TL tumour size at Week 16 will also be performed using the non-parametric method of an ANCOVA model on the ranked percentage change in tumour size with the same factors and covariates listed above. Ranking will be performed on the analysis data set following appropriate imputation of missing data:

- the patient with the greatest percentage reduction in TL tumour size at Week 16 will be assigned the lowest rank, with smaller changes and increases in tumour sizes taking increasing ranks
- deaths prior to the end of the window used to select Week 16 data will be assigned the highest rank (i.e. those patients for whom a value equal to the maximum percentage change in TL tumour size was imputed because the patient died).

The p-value from the non-parametric ANCOVA model will be presented together with the Hodges-Lehmann estimate of the median difference and corresponding 90% CI. The median, minimum and maximum percentage change will be presented for each treatment arm, together with the number of patients and percentage of patients in each treatment arm whose Week 16 data is imputed in the non-parametric analysis.

A sensitivity analysis of percentage change from baseline in TL tumour size at Week 16 using site investigator data will be performed in the same way as described above.

In addition, a descriptive summary table and a waterfall plot for best percentage change in TL tumour size will be provided.

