8.5.2 Secondary analyses

Secondary analyses will be performed for the patient populations defined earlier, and according to the overview below.

Patient Population	Secondary Objectives	Outcome Measures

 • HRR_m • All 	To assess the efficacy of the combination of ceralasertib +olaparib and the combination of AZD1775+olaparib compared with olaparib monotherapy by assessment of PFS	PFS using Blinded Independent Central Review (BICR) according to Response Evaluation Criteria in Solid Tumours (RECIST 1.1) Sensitivity analysis of PFS using Investigator assessments according to RECIST 1.1

Patient Population	Secondary Objectives	Outcome Measures

 • BRCAm • HRRm • Non BRCAm HRRm • All • Non HRRm 	
To assess the efficacy of the combination of ceralasertib +olaparib and the combination of AZD1775+olaparib compared with olaparib monotherapy in terms of
 
 • ORR 	
Objective response using BICR according to RECIST 1.1 Sensitivity analysis of objective response using Investigator assessments according to RECIST 1.1

 • BRCAm • Non BRCAm HRRm • Non HRRm 	
To assess the efficacy of the combination of ceralasertib +olaparib and the combination of AZD1775+olaparib compared with olaparib monotherapy in terms of
 
 • DoR • tumour change 	
DoR and tumour change using BICR according to RECIST 1.1 Sensitivity analysis of DoR, and tumour change using Investigator assessments according to RECIST 1.1

 • BRCAm • HRRm • Non BRCAm HRRm • All • Non HRRm 	
To assess the efficacy of the combination of ceralasertib +olaparib and the combination of AZD1775+olaparib compared with olaparib monotherapy in terms of OS
	
Time to death for any cause

 • BRCAm • HRRm • Non BRCAm HRRm • All • Non HRRm 	
To compare the efficacy of the combination of ceralasertib +olaparib with the combination of AZD1775+olaparib in terms of
 
 • PFS • ORR 	
PFS and objective response using BICR according to RECIST 1.1 Sensitivity analysis of PFS and objective response using Investigator assessments according to RECIST 1.1

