
 • BRCAm • Non BRCAm HRRm • Non HRRm 	
To compare the efficacy of the combination of ceralasertib +olaparib with the combination of AZD1775+olaparib in terms of
 
 • DoR • tumour change 	
DoR and tumour change using BICR according to RECIST 1.1 Sensitivity analysis of DoR and tumour change using Investigator assessments according to RECIST 1.1

 • BRCAm • HRRm • Non BRCAm HRRm • All • Non HRRm 	
To compare the efficacy of the combination of ceralasertib +olaparib with the combination of AZD1775+olaparib in terms of OS
	
Time to death for any cause

Patient Population	Secondary Objectives	Outcome Measures

 All 	To explore the frequency of and describe the nature of tumour HRR (including BRCA) mutation(s) in tumour samples and to compare this with germline HRR (including BRCA) mutation status	Tumour and germline mutation status of CC1 genes

 All 	To assess exposure to olaparib, ceralasertib and AZD1775 in all patients	$C_{\min ss}$

For patient populations based on single tumour gene-based strata, unweighted analyses will be conducted; for patient populations based on a combination of tumour gene-based strata, weighted analyses (with weights derived as described in Section 8.5.1) will be conducted.

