8.5.2.1 Analysis of objective response

Objective response will be analysed using logistic regressions with a covariates study treatment and prior platinum-based therapy. The results of the analysis will be presented in terms of an odds ratio for study treatments together with associated 90% profile likelihood CI and 2-sided p-values. P-values will be based on twice the change in log-likelihood resulting from the addition of covariate study treatment to the model containing only the covariate related to prior platinum-based therapy.

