1.2.3 Randomisation

Eligible patients will be randomised (using randomisation ratio 1:1:1) to Olaparib monotherapy, AZD6738+Olaparib or AZD1775+Olaparib. Effective April 2019, eligible patients will be randomised (using randomisation ratio 1:1) to Olaparib monotherapy or AZD6738+Olaparib.

The randomisation scheme will be stratified based on:

- the primary patient population: stratum A (*BRCAm*), stratum B (non *BRCAm* HRR m), stratum C (non HRR m) as defined in Section 1.2.1
- and patient's prior platinum-based therapy (no / yes)

so that there will be a total of 6 strata: An, Ay, Bn, By, Cn, Cy.

The 3 primary patient populations A, B, C will be capped to have approximately 150 patients each (approximately 50 patients per treatment arm). It is expected that the non-HRR m patient population will be recruited fastest.

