6. CHANGES OF ANALYSIS FROM PROTOCOL

Not applicable.

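### For the pooled HRRm and All populations the SAP's response-rate model has no stratum weights and no biomarker term, although protocol 8.5.2 requires weighting and SAP section 6 declares no change

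*SAP*

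**What the plan says.** **Protocol.** The table in section 8.5.2 lists "Objective response using BICR according to RECIST 1.1" for all five populations, including HRRm (strata A and B) and All (A, B and C). The rule below the table keeps unweighted analyses for single strata. Otherwise, "for patient populations based on a combination of tumour gene-based strata, weighted analyses (with weights derived as described in Section 8.5.1) will be conducted". Section 8.5.1 takes the weights from external literature and the screening records. Section 8.5.2.1 then gives the response model: "Objective response will be analysed using logistic regressions with a covariates study treatment and prior platinum-based therapy".

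**SAP.** Section 4.2.8.3, headed for all five populations, states "Objective response will be analysed using logistic regression with covariates study treatment and prior platinum-based therapy (no/yes". Its likelihood-ratio p-value compares that model with one whose only covariate is prior platinum, so biomarker stratum does not enter. The ORR row of the overview in 4.2.7 agrees: "Logistic regression model with covariates study treatment and prior platinum-based therapy".

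Pooled PFS is treated differently. Section 4.2.8.1 combines stratum log hazard ratios with the weights for HRRm and adds an unweighted analysis stratified by biomarker population and prior platinum. Section 4.2.8.2 extends this to All: "Similar summaries and weighted and unweighted analyses as described in Section 4.5.2.1 will be conducted for the All patient population". (The SAP has no section 4.5.2.1; 4.2.8.1 is presumably meant.) The output list has separate weighted and unweighted tables for pooled PFS, but a single logistic table for BICR response covering all five populations.

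Section 6, "CHANGES OF ANALYSIS FROM PROTOCOL", reports none.

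**The concern.** The strata are filled by design: "The 3 primary patient populations A, B, C will be capped to have approximately 150 patients each". A pooled, unweighted odds ratio therefore describes a roughly equal mix of strata. The weights exist so that pooled results represent the intended population. As written, HRRm and All would mean one population for the main PFS result and another for ORR in the same report.

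Leaving biomarker stratum out of the model has three further effects:

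- If response rates differ by stratum and the odds ratio is common and not 1, the pooled odds ratio lies closer to 1 than the within-stratum value.
- If odds ratios differ by stratum, the pooled value can fall on either side of the weighted one.
- The AZD1775 arm closed early and probably has a different stratum mix, so its pooled comparisons, which 4.2.8.3 lists, can be confounded by stratum.

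**Working it through.** **1. Text.** The conflict rests on the wording, and neither document gives an ORR figure to reproduce. Protocol 8.5.2 and 8.5.2.1 can be read together: fit the 8.5.2.1 model within each stratum, then combine with the 8.5.1 weights. Reading 8.5.2.1 as overriding 8.5.2 would leave the weighting sentence almost empty. Pooled PFS is already weighted under 8.5.1, OS inherits that through 8.5.2.4, and DoR and tumour change are analysed only in single strata. Version timing does not explain the gap. SAP 2.0 was updated for protocol 6.0, and the protocol's version history lists no later change to 8.5.2.

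**2. Inputs for size.** From the documents: 50 patients per arm per stratum, and two-sided 10% tests. Assumed: olaparib ORRs of 60/20/10% in A/B/C, the odds ratios and the weights. The 60% is suggested by the 59.9% in protocol 1.2.1, which is for all patients in a trial of mixed TNBC and hormone-receptor-positive BRCA-mutated disease. A flatter set, 41/24/24%, uses the ovarian rates with and without BRCA mutation in the same section. Prior platinum is left out.

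**3. Common odds ratio of 2.0.** The combination-arm rate is 2·odds/(1 + 2·odds).

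- 60/20/10% becomes 75.0/33.3/18.2%.
- All: the means are 30.0% and 42.2%, so OR = (0.4217/0.5783)/(0.30/0.70) = **1.70**. The log OR is 23% smaller than ln 2.
- HRRm: the means are 40.0% and 54.2%, so OR = 1.1818/0.6667 = **1.77**, 17% smaller.
- 41/24/24%: OR is 1.95 in both, 3–4% smaller.

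**4. Different odds ratios, All, 60/20/10%.** Weighted OR = exp(Σ w·ln OR).

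| ORs in A/B/C | Unweighted | Weighted 15/15/70 |
|---|---|---|
| 3.0/1.5/1.0 | 1.54 | exp(0.15·1.099 + 0.15·0.405) = 1.25 |
| 1.0/1.5/3.0 | 1.40 | exp(0.15·0.405 + 0.70·1.099) = 2.29 |

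In the first row the weighted value is 1.16 at weights 10/10/80 and 1.35 at 20/20/60.

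**5. Precision, All, common OR 2.0, 60/20/10%.** The stratum variances of the log OR (sums of reciprocal expected counts) are 0.190, 0.215 and 0.357.

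- Weighted 15/15/70: 0.0225·0.190 + 0.0225·0.215 + 0.49·0.357 = 0.184, SE 0.43.
- Stratum-adjusted (approximated by inverse variance): 1/(5.26 + 4.65 + 2.80) = 0.0786, SE 0.28. The variance ratio is 2.3.
- Power in All: SAP model about 74% (simulation), stratum-adjusted about 80%, weighted about 49% at 15/15/70, about 42% at 10/10/80 and about 77% at equal weights.
- Power in HRRm: SAP model about 67%, stratum-adjusted about 70%, weighted 63–70% for weights between 30/70 and 70/30.

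**6. Test level under no effect.** With strata balanced across arms, the unadjusted test uses variance 0.30·0.70 = 0.21 per patient, where the true within-stratum mean is (0.24 + 0.16 + 0.09)/3 = 0.163. The effective cut-off is 1.645/√(0.163/0.21) = 1.87, a rejection rate of about 6% at a nominal 10% (simulation agrees). At 41/24/24% the simulated rate is close to 10%.

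**7. AZD1775 arm.** About 350 patients in total (SAP 1.3) less about 300 in the other two arms leaves about 50. SAP 5.2 puts about 25 of them in stratum C. Splitting the rest equally (assumed) gives a mix of 25/25/50.

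- With no true effect at 60/20/10%, the arm's pooled rate is 0.25·0.60 + 0.25·0.20 + 0.50·0.10 = 0.250 against 0.300 on olaparib, so OR = 0.333/0.429 = **0.78**.
- At 41/24/24% the rates are 0.2825 and 0.2967, OR 0.93.

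**The case against.** The strongest reply is that SAP 4.2.8.3 follows protocol 8.5.2.1 almost exactly: same covariates, same likelihood-ratio test, same profile-likelihood interval. The protocol writes out a weighting formula only for the log hazard ratio. On that view the SAP shares an omission with the protocol, and section 6 is defensible for the model itself. This stands for the covariate list. It does not remove the 8.5.2 rule, which the SAP applies to PFS and not to ORR.

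A second reply is that the pull towards 1 is largely non-collapsibility. For ceralasertib plus olaparib against olaparib, stratified randomisation balances the strata, so the marginal odds ratio is a different estimand and not a biased one. That is right, and the null test is conservative, not inflated. Which estimand is meant should still be stated, and the marginal one is tied to the capped mix.

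Third, the large contrasts come from assumed rates, weights and odds ratios; at 41/24/24% the shift under a common odds ratio is only 3–4%. Weighting All can also be expensive, since it leans on stratum C, where about 5 and 9 responders are expected per arm at a 10% olaparib rate. Both points stand and bear on the choice of main analysis. No passage requires a biomarker term for ORR; the argument for it is that stratum is a randomisation factor and already enters the unweighted pooled PFS analysis.

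**Conclusion.** The concern holds. Protocol 8.5.2 requires weighted analyses for ORR in HRRm and All, the SAP specifies none, and section 6 declares no change. The missing biomarker term is a further weakness and not a departure from the protocol.

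The numerical effect depends on rates and weights that the documents do not give. It is small if response rates are similar across strata and material if rates or effects differ strongly. The AZD1775 figures also rest on an assumed stratum mix and concern an arm for which the study is no longer sized.

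Pooled ORR is secondary and outside the multiplicity control, and each single stratum is reported as well. The primary PFS analyses are not affected. The SAP should be corrected before the pooled ORR analyses are run.

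**What to change.** In SAP 4.2.7, 4.2.8.3 and the output list, for HRRm and All:

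1. Estimate platinum-adjusted log odds ratios within each biomarker stratum and combine them, with their variances, using the PFS weights: Σ w·ln OR and Σ w²·var.
2. Also report an unweighted logistic model with biomarker stratum added as a covariate, matching the weighted and stratified pair used for pooled PFS.
3. Name a fallback for strata with few responders that still yields a log odds ratio, such as penalised likelihood. The present Fisher fallback gives only a p-value and cannot feed the weighted estimate.
4. If the stratum-adjusted model is preferred as the main analysis for precision, say so and give the reason in section 6.

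Separately, SAP 4.2.8.6 sends Non HRRm and All to the pooled methods for OS; HRRm and All must be meant.

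The cost is SAP wording and minor programming. No new data are needed, and the weights are already required for PFS. The statistical price is the precision lost by weighting All. The case for weighting is the estimand and consistency with the protocol; the power gain belongs to the stratum-adjusted model.
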